#### **7.7 Premature termination of the study**

The investigators can decide to terminate the study premature for urgent medical reasons. For example in the case of a high amount of unexpected serious side effects.

## 8. SAFETY REPORTING

### 8.1 Temporary halt for reasons of subject safety

In accordance to section 10, subsection 4, of the WMO, the sponsor will suspend the study if there is sufficient ground that continuation of the study will jeopardise the subject's health or safety. The sponsor will notify the accredited METC without undue delay of a temporary halt including the reason for such an action. The study will be suspended pending a further positive decision by the accredited METC. The investigator will take care that all subjects are kept informed.

### 8.2 AEs, SAEs and SUSARs

#### 8.2.1 Adverse events (AEs)

Adverse events are defined as any undesirable experience occurring to a subject during the study, whether or not considered related to the fasting mimicking diet or food supplement. At every study visit the occurrence of an adverse event is evaluated. A telephone number is provided to all the subjects in the study in the informed consent form which they can contact in case of an (serious) adverse event during the study. All adverse events reported at the study visit by the subject or observed by the investigator or the research staff will be evaluated and recorded.

The occurrence of hypoglycemia is evaluated at every study visit in all intervention groups together with the glucose monitoring. Patients in the diet group that use sulfonylureas or insulin are instructed to call the investigator in case of hypoglycemia (see paragraph 5.3). In case of persistent or severe hypoglycemia, patients can contact the investigator on week days and the internal resident on duty at the Haaglanden Medical Center in the evening/night of weekdays and on weekend days. Treatment of hypoglycemia will be performed according to the investigator's or physician's decision and the guidelines of hypoglycemia.

Any (serious) adverse event recorded by the general practitioner or internal residents at the Haaglanden Medical Center will be reported to the investigator by email ([name] ) or by telephone as soon as possible. The investigator is responsible for evaluating and recording all adverse events.

The laboratory results will be evaluated by the investigator. An abnormality in a laboratory assessment will be documented and is left to the discretion of the investigator. If, in the opinion of the investigator, the laboratory results jeopardise the safety of the subject, the subject will be withdrawn from the study. The following results or references ranges will require additional investigation and follow-up:

- ASAT and ALAT level  $\geq$  than two times the baseline value.
- Creatinine level increase of more than 25% of the baseline value.
- CRP level  $\geq$  10 mg/dl.

### 8.2.2 Serious adverse events (SAEs)

A serious adverse event is any untoward medical occurrence or effect that

- results in death;
- is life threatening (at the time of the event);
- requires hospitalisation or prolongation of existing inpatients' hospitalisation;
- results in persistent or significant disability or incapacity;
- is a congenital anomaly or birth defect; or
- any other important medical event that did not result in any of the outcomes listed above due to medical or surgical intervention but could have been based upon appropriate judgement by the investigator.

An elective hospital admission will not be considered as a serious adverse event.

All adverse events during the study reported or observed by the subject, investigator, general practitioner or internal residents at the Haaglanden Medical Center will be evaluated by the investigator for the criteria of a SAE. All serious adverse events will be recorded in SAE report forms by the investigator and send to the sponsor without undue delay after obtaining knowledge of the events. The sponsor will report the SAEs through the web portal *ToetsingOnline* to the accredited METC that approved the protocol, within 7 days of first knowledge for SAEs that result in death or are life threatening followed by a period of maximum of 8 days to complete the initial preliminary report. All other SAEs will be reported within a period of maximum 15 days after the sponsor has first knowledge of the serious adverse events. All SAE report forms will be stored in the trial master file.

### 8.3 Annual safety report

The sponsor will submit, once a year throughout the clinical trial, a safety report to the accredited METC, competent authority, and competent authorities of the concerned Member States.

This safety report consists of:

- a list of all suspected (unexpected or expected) serious adverse reactions, along with an aggregated summary table of all reported serious adverse reactions, ordered by organ system, per study;
- a report concerning the safety of the subjects, consisting of a complete safety analysis and an evaluation of the balance between the efficacy and the harmfulness of the medicine under investigation.

**8.4 Follow-up of adverse events**

All adverse events will be followed until they have abated, or until a stable situation has been reached. Depending on the event, follow up may require additional tests or medical procedures as indicated, and/or referral to the general physician or a medical specialist. SAEs need to be reported till end of study within the Netherlands, as defined in the protocol.

## 9. STATISTICAL ANALYSIS

### 9.1 Primary study parameter

SPSS will be used for all statistical analysis. Data analysis will be performed based on the intention to treat principle. Patients will be included in the analyses according to the treatment to which they were randomised.

The primary endpoint Microvascular Health index (MHI) will be summarized in mean with standard deviation or median with interquartile range. The effect within the group between baseline and 3 months is tested using a paired Student's t test (two-tailed). Differences in improvement of the MHI between baseline and 3 months between the FMD group and the placebo group and the food supplement and placebo group will be tested with an independent Student's t test.

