**Intervention:** One group receives a monthly 5-day fasting mimicking diet, one group receives daily 4 capsules of a food supplement and one group receives daily 4 placebo capsules, all for 3 consecutive months.

**Main study parameters:** The primary endpoint is an improvement of the Microvascular Health index in the diet group compared to the placebo group and in the food supplement group compared to the placebo group, after 3 months of the intervention.

Secondary endpoints: reduce albuminuria, decrease inflammation (urinary heparanase and MCP-1 expression, serum CRP and MCP-1 levels), reduce occurrence of specific urinary HS domains, improve metabolic parameters; fasting glucose, HbA1c, C-peptide, IGF-1, total cholesterol, LDL cholesterol, HDL cholesterol, and triglycerides serum levels, waist circumference, waist-to-hip ratio, body weight and systolic blood pressure after 3 months of the fasting mimicking diet and after 3 months of the food supplement.

The legacy effect of the interventions is also determined, 3 months after stopping with the intervention.

**Nature and extent of the burden and risks associated with participation, benefit and group relatedness:** Eligible patients are randomly assigned to the fasting mimicking diet, food supplement or placebo arm. At baseline, after 3 months and at 6 months, the MHI is measured by non-invasive SDF imaging of the microcirculation under the tongue, and blood and urine samples are collected. In the FMD arm, dosages of the hypoglycemic drugs are adapted during the 5 days of the diet prevent hypoglycemia. Glucose monitoring is done during the diet and at the end of each month in all intervention arms through a finger prick blood sample.

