### 3. STUDY DESIGN

A 6-month, single center randomized controlled trial to study the effects of dietary interventions on improving endothelial health in South Asian patients with diabetic nephropathy. In total 90 South Asian patients with type 2 diabetes and proven microalbuminuria between 18-75 years of age will be recruited at general practitioner centers in the The Hague region. Eligible patients will be included for a period of 6 months. Patients will be randomly assigned to receive the fasting mimicking diet, food supplement or placebo for a period of 3 months. The primary endpoint is an improvement of the Microvascular Health index after 3 months in the diet group compared to the placebo group and in the food supplement group compared to the placebo group, measured with SDF-imaging. After 6 months, which is 3 months after stopping with the interventions, patients will also return for a follow-up measurement to investigate possible legacy effects of each intervention.

The food supplement and placebo arm will be double blinded. The placebo arm will also be used as a control group for the FMD arm.

Study procedures will take place at the practice of the general practitioner and will be performed by LUMC research staff. The general practitioner will not perform any of the study procedures. Flow chart I gives an overview of the study design and time points for study visits.

Flow chart I

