#### **4.4 Sample size calculation**

The primary outcome will be improvement of the Microvascular Health Index after 3 months. The sample size is chosen according to a pilot study with 13 healthy volunteers receiving the food supplement Endocalyx™ for 3 consecutive months. After 3 months, a 31% improvement in Microvascular Health Index was demonstrated, expressed in a significant increase of the MHI from 1.05 at baseline, to 1.38 at 3 months (improvement of 0.33).

Group sample sizes of 23 per group achieve 80% power to detect a difference of 0.35 between the null hypothesis that group improvement means are 0.0 and the alternative hypothesis that the improvement mean of group 2 or 3 is 0.35 with estimated group standard deviations of 0.41 with a significance level (alpha) of 0.05000 using a two-sided two-sample t-test. If we anticipate a 25% drop out rate per group, we will need 30 patients per group.

Therefore, we decided to enrol a total number of 90 patients in this study.

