## 7. METHODS

### 7.1 Study parameters/endpoints

#### 7.1.1 Main study parameter/endpoints

The primary endpoint is to improve the endothelial microvascular health expressed by an improvement in Microvascular Health Index between baseline and 3 months of treatment in South Asian patients with type 2 diabetes mellitus through:

1. The fasting mimicking diet in comparison to the placebo.
2. The endocalyx food supplement in comparison to the placebo.

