### 9.2 Secondary study parameters

The categorical data will be summarized by the frequencies and percentages and tested within the group between baseline and 3 months using a Pearson's Chi-squared test. The continuous data will be summarized in mean with standard deviation in case of normal distribution or median with interquartile range in case of non-normal distribution. A paired two-tailed Student's t test or Wilcoxon signed rank test will be used to calculate the effect within the group between baseline and 3 months.

Differences in outcomes between the groups (diet vs placebo and supplement vs placebo) will be tested with a Student's t test for normally distributed data or Mann-Whitney *U* test for non-normally distributed data.

A paired two-tailed Student's t test or Wilcoxon signed rank test for differences of the primary and secondary parameters between baseline and 6 months within the group will be used to evaluate the legacy effect of the interventions 3 months after stopping with the intervention.

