### 9.3 Other study parameters

Demographic data and other baseline characteristics will be summarised using descriptive statistics. The main analyses will also be performed in a priori defined subgroup analyses such as age at baseline, smokers vs non-smokers ect.

Additional explorative analyses involve the analysis of prognostic and predictive factors for achieving the primary or secondary endpoint, this will be investigated by using logistic regression. The level of significance for all tests will be set at  $p<0.05$ .

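### Do the unranked paired tests in Section 9.1, and the lack of a rule for a split result, leave the primary analysis undecided?

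*Combined protocol and SAP*

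**What the plan says.** Section 9.1, on the primary parameter, names two kinds of test. The first is within each arm: "The effect within the group between baseline and 3 months is tested using a paired" Student's t test. The second is the comparison of improvement "between the FMD group and the placebo group and the food supplement and placebo group will be tested with an independent" Student's t test. Section 9.3 applies one threshold throughout: "The level of significance for all tests will be set at" p<0.05. The paired tests are not labelled supportive.

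The endpoint is described in several places:

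- The Summary states one primary endpoint, improvement "in the diet group compared to the placebo group and in the food supplement group compared to the placebo group". Section 3 says the same and adds: "The placebo arm will also be used as a control group for the FMD arm".
- Section 2 lists two numbered primary objectives, one per intervention, each against placebo.
- Section 7.1.1 again numbers two comparisons, the first being "The fasting mimicking diet in comparison to the placebo".
- Section 4.4 sizes the trial with a two-sided two-sample t test, under "the alternative hypothesis that the improvement mean of group 2 or 3 is 0.35".

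Section 9.2 adds a six-month analysis, in which paired tests "between baseline and 6 months within the group will be used to evaluate the legacy effect of the interventions".

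**The concern.** Two things look wrong on a first reading of Section 9.1.

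First, a paired test does not address an endpoint defined against placebo, yet it comes first under the primary parameter and uses the same 5% level. If MHI rose equally in all arms, an intervention arm could show a significant change from baseline with no benefit over placebo. Such a rise is conceivable, because Sections 5.2 and 5.3 allow background drugs to be altered. The fear is that a within-arm p-value would be reported as the primary result.

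Second, the wording of success seems to vary: *and* in the Summary and Section 3, *or* in Section 4.4, and two numbered items in Sections 2 and 7.1.1. If *and* meant that both comparisons must succeed, or *or* that either is enough, the power and error rate would differ from those in Section 4.4. A split result would then be read differently depending on which section one consults.

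**Working it through.** **Inputs.** Section 4.4 gives a difference of 0.35, an SD of improvement of 0.41, 23 per group, two-sided alpha 0.05 and 80% power. The simulated figures below assume normal changes, equal SDs and 23 evaluable patients in each of three arms.

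**1. The plan's own figure.** The standardised difference is 0.35/0.41 = 0.854. The noncentral t calculation for two groups gives n = 22.54, so 23 per group, with power 80.8%. This reproduces Section 4.4. The stated 80% is therefore the power of one two-sample comparison with placebo.

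**2. What each reading of success would imply.** If both interventions truly give 0.35:

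| Reading | Chance of success |
|---|---|
| Each comparison as its own question | 80.8% each |
| Both required | about 70% |
| Either sufficient | about 92% |

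The figures agree with each other: 0.698 + 0.918 = 1.616 = 2 × 0.808. Exactly one comparison succeeds in 0.918 − 0.698 = 22.0% of trials. If only one intervention works, exactly one comparison shows benefit in 78%. Split results are therefore realistic. Only the first reading matches the 80% in Section 4.4.

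**3. Error rates with no change in any arm.** At least one of the two placebo comparisons is significant in either direction in about 9.1% of trials, and shows false benefit in about 4.5%. At least one of all five tests is significant in about 17.5%.

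**4. Equal drift in all arms (assumed; the documents give no placebo-arm change).** For one arm, the chance of a significant within-arm rise is 0.081, 0.200, 0.455 and 0.609 at drifts of 0.05, 0.10, 0.165 (half the pilot's 0.33) and 0.20. For at least one of the two intervention arms, 1 − (1 − p)² gives about 16%, 36%, 70% and 85%. False benefit against placebo stays near 4.5% throughout.

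**5. Which of these rates belong to the plan.** The 17.5% and the drift figures apply only if a paired p-value can establish the primary endpoint. No section allows that: the endpoint is relative to placebo in the Summary and in Sections 2, 3 and 7.1.1, and the sample size rests on the between-group test. The tests that decide are the two placebo comparisons, and drift common to all arms leaves their error rate unchanged.

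**6. The *and* and *or* wording.** In the Summary and Section 3, *and* joins two items in a list of comparisons. In Section 4.4, *or* sits inside the description of a single two-group test and says that the calculation serves whichever intervention group is compared with placebo. Neither is a rule for combining results. Sections 2 and 7.1.1 number the comparisons, and Section 9.1 tests them separately. The plain reading is two questions, each at two-sided 0.05. Leaving them unadjusted is defensible because they concern two different interventions.

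**The case for a change.** The best case for a change is that Section 9.2 shows the authors do treat a within-arm p-value as evidence of effect. The legacy effect at six months, for MHI as well as the secondary parameters, is assigned to paired tests. The diet arm is also unblinded, so a success rule chosen after a split result could not be shown to be prespecified. A labelling sentence in Section 9.1 would cost no patients, power or alpha.

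Some of this stands. Section 9.1 does not call the paired tests descriptive, and no sentence states outright that the two placebo comparisons are separate claims. The remark about Section 9.2 is also fair. There a within-arm test does carry the stated inference, although the between-group sentence in that section names no time point and could be applied at six months as well. That is a separate question about a later analysis. Relabelling the tests in Section 9.1 would not settle it, and it does not affect the three-month primary conclusion.

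The rest is weaker. If the comparisons are two numbered objectives, a split result needs no further rule: one objective is met, the other is not, and both are reported. Replacing a paired p-value by a 95% confidence interval for mean change would not alter the evidence, since the interval excludes zero exactly when the two-sided paired test has p<0.05. The drift mechanism has thin support too. Section 5.3 leaves glucose-lowering doses unaltered at monthly visits when fasting glucose is 4.0 to 15.0 mmol/L without hypoglycemia, and names only hypoglycemia or a lower value as a reason to alter them. Section 5.2 prefers that RAAS inhibitors stay as they are.

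**Conclusion.** No change to the plan is needed on this point. Read as a whole, the documents say which tests decide: the two comparisons of MHI change with placebo, each its own question at two-sided 0.05, and each with 80.8% power at 23 per arm if the difference is 0.35 and the SD 0.41. The 70% and 92% describe joint rules, and the 17.5% and the assumed drift results describe a within-arm decision rule. The plan contains none of these, so they should not be quoted as properties of its primary analysis. What remains is missing detail: a label for the paired tests and an explicit statement that the two comparisons stand apart. An analyst following Sections 2, 4.4 and 7.1.1 would supply both correctly and reach the same primary conclusion. This rests on reading the numbered objectives as separate claims, which the documents support but do not state in so many words.

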#### **7.5 Replacement of individual subjects after withdrawal**

The sample size calculation for this study is given in paragraph 4.4. A 25% protocol violator and/or drop-out rate is taken into account. Therefore an inclusion of 30 subjects per study group is aimed. However, drop-outs from this study that occur during the first 2,5 months because of schedule problems, pregnancy or non-diabetic medical reasons may be replaced in order to reach 23 subjects per study group to complete the study. If a subject discontinues from the study prematurely the reason must be fully evaluated and recorded appropriately in

source documentation and the eCRF. If the subject is being withdrawn because of an AE, that AE must be indicated as the reason for withdrawal.

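### The primary MHI comparison is valid but does not adjust for baseline MHI; a prespecified ANCOVA would usually be more precise at almost no cost

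*Combined protocol and SAP*

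**What the plan says.** - **Primary test.** Section 9.1 takes "Differences in improvement of the MHI between baseline and 3 months" and says that these differences "between the FMD group and the placebo group and the food supplement and placebo group will be tested with an independent" Student's t test. No covariate is named.
- **Endpoint.** Section 7.1.1 defines it as "improvement in Microvascular Health Index between baseline and 3 months of treatment", so the change score and the endpoint agree.
- **Baseline data.** The Summary states: "At baseline, after 3 months and at 6 months, the MHI is measured by non-invasive SDF imaging". Section 10.3 likewise gives three SDF imaging time points in all arms.
- **Sample size.** Section 4.4 uses a two-sided two-sample t test at alpha 0.05 with 23 per group, and "the alternative hypothesis that the improvement mean of group 2 or 3 is 0.35 with estimated group standard deviations of 0.41".
- **Other analyses.** Section 9.3 adds subgroup repeats and an exploratory logistic regression. Neither adjusts the primary contrasts for baseline MHI, and no other section does.

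**The concern.** Subtracting baseline from follow-up is one way of using the baseline value, but it assumes that each unit of baseline MHI carries over in full to 3 months. If the true slope is below 1, as measurement noise and regression to the mean tend to make it, the change score over-corrects and carries avoidable variance. It also leaves part of any chance baseline imbalance in the estimate, and section 7.2 names no stratification by baseline MHI.

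The stake is precision. Planned power is only just above 80%, and each contrast has a 95% CI half-width of 0.244 against a target of 0.35. A measurement already paid for could narrow that interval, but the choice has to be written down before the data are seen if it is to be credible.

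**Working it through.** **Inputs from section 4.4:** difference 0.35, SD 0.41 (read as the SD of improvement), 23 per arm, two-sided alpha 0.05. **Assumed, because the documents do not give them:** ρ, the correlation of baseline and 3-month MHI; and k, the ratio of follow-up SD to baseline SD.

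**1. The plan's own figure.** SE = 0.41 × √(2/23) = 0.1209 on 44 df. The noncentrality is 0.35/0.1209 = 2.89, giving power 80.8%; 22 per arm gives 79.0%. The stated 23 per group is reproduced. CI half-width = 2.015 × 0.1209 = 0.244.

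**2. ANCOVA formulas.** Baseline SD s = 0.41/√(1 + k² − 2ρk). Slope β = ρk. Residual variance = k²s²(1 − ρ²). It follows that 0.41² minus the residual variance equals (1 − β)²s², which is never negative. The only loss comes from estimating the slope: a variance inflation of 1 + 1/(2×22 − 2) = 1.0238, and 43 df instead of 44.

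**3. Example, k = 1, ρ = 0.5.** Residual SD = 0.41 × √0.75 = 0.355. SE = 0.355 × √(1.0238 × 2/23) = 0.106. Power is 89.8% and half-width 2.017 × 0.106 = 0.214.

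**4. Range at 23 per arm.** Each cell shows the net variance reduction, then power (planned: 80.8%).

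| k | ρ = 0.3 | ρ = 0.5 | ρ = 0.7 | ρ = 0.9 |
|---|---|---|---|---|
| 0.8 | 49%; 97.7% | 42%; 95.9% | 36%; 94.2% | 38%; 94.8% |
| 1 | 33.5%; 93.4% | 23.2%; 89.8% | 13.0%; 85.8% | 2.7%; 81.8% |
| 1.15 | 24.5%; 90.3% | 13.4%; 86.0% | 3.1%; 82.0% | −1.9%; 80.1% |
| 1.25 | 19.7%; 88.4% | 8.6%; 84.1% | −0.4%; 80.6% | 2.7%; 81.8% |

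For k = 1 the half-widths are 0.199, 0.214, 0.227 and 0.240. The worst case is β = 1 exactly (for example k = 1.25, ρ = 0.8): variance rises 2.4%, power is 79.9% and half-width 0.247.

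**5. Simulation, k = 1.** With 40,000 trials per setting, two-arm ANCOVA power was 93.5, 89.8, 85.7 and 81.8% at ρ = 0.3, 0.5, 0.7 and 0.9, with mean estimate 0.35. In a separate run of 20,000 trials per setting at ρ = 0.3, 0.5 and 0.8, type I error was 4.8 to 5.0% for the t test and 5.0 to 5.2% for ANCOVA.

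**6. Chance imbalance, k = 1.** A baseline difference of one standard error shifts the change-score estimate by (1 − ρ) × s × √(2/23): 0.5 × 0.41 × 0.295 = 0.060 at ρ = 0.5, and 0.3 × 0.529 × 0.295 = 0.047 at ρ = 0.7.

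**7. Which ANCOVA.** Suppose the FMD residual SD is 1.5 or 2 times that of the other arms (assumed; ρ = 0.7, 23 per arm). Simulated type I error is then:

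| Model | FMD–placebo | Supplement–placebo |
|---|---|---|
| Planned t test | 4.8 / 5.2% | 5.0 / 4.9% |
| Two-arm ANCOVA | 5.1 / 5.3% | 5.0 / 5.0% |
| Three-arm, HC3 errors | 4.7 / 4.8% | 4.5 / 4.3% |
| Three-arm, one pooled variance | 6.6 / 8.0% | 2.1 / 0.7% |

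With 27 placebo and 19 FMD completers (assumed) and the same SD ratios, FMD–placebo type I error is 6.5 / 7.6% for the t test, 6.6 / 7.7% for two-arm ANCOVA and 4.5 / 4.5% for two-arm ANCOVA with HC3 errors.

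**The case against.** **There is no defect.** Sections 4.4, 7.1.1 and 9.1 agree with each other, and the planned test is unbiased and delivers its stated power. The proposed primary analysis could even leave power at 79.9%. This is correct, and it is why the point is a recommended improvement only. The trade is uneven, though: at most 0.9 points of power lost, against 1 to 13 points gained when the visit SDs are equal.

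**The gain rests on unknowns.** The pilot mean in section 4.4 rose from 1.05 to 1.38 on an index bounded below by 0, so a follow-up SD larger than the baseline SD is plausible. The table then shows gains near nil or slightly negative at ρ of 0.7 and above with k modestly over 1. This stands: no single gain should be quoted. No cell falls below the 79.9% bound.

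**The SD of 0.41 is not labelled.** If it were the SD at one visit (equal at both), t-test power would be 67, 81 and 95% at ρ = 0.3, 0.5 and 0.7, against 83, 90 and 97% for ANCOVA. The 80.8% reference depends on the reading; the direction of the result does not.

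**The variance and completer scenarios are hypothetical.** They are. They bear on the form of the ANCOVA, not on whether to adjust.

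**Conclusion.** The point holds as an efficiency improvement. The plan's t test on change is valid and its sample size is consistent with it, but baseline MHI is collected and then used less well than it could be. With equal visit SDs and ρ from 0.3 to 0.9, ANCOVA cuts variance by a net 33.5% to 2.7% and moves power from 80.8% to between 93.4% and 81.8%. The gain is larger if the follow-up SD is below the baseline SD, and can vanish if it is above. The downside is bounded at a 2.4% variance increase.

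These figures assume that 0.41 is the SD of improvement, 23 completers per arm, and a linear slope common to the arms. How missing 3-month MHI is handled is a separate matter.

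**What to change.** In section 9.1, prespecify as primary a separate two-arm ANCOVA for FMD–placebo and for supplement–placebo: 3-month MHI on randomised arm, with baseline MHI as covariate, reported as an adjusted difference with 95% CI. The endpoint is untouched: with baseline in the model, the arm coefficient is the same whether the response is 3-month MHI or the change.

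Keep the change-score t test as a sensitivity analysis. Add HC3 standard errors as a second one, since section 7.5 allows for a 25% loss and completers may differ between arms.

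One three-arm model with HC3 errors is an acceptable alternative. A three-arm model with a single pooled residual variance is not, because the third arm would then help set the error term of each contrast.

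The cost is one degree of freedom, about 2.4% variance inflation for the estimated slope, and a linear common-slope assumption. No new data or patients are needed, and the sample size need not change.
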